¹¹ P4 provided as part of this study contains peanut oil and should never be used by subjects with allergy to peanuts

Unless otherwise noted, baseline is defined as the last non-missing value recorded prior to the first dose of trial drug. Unscheduled visits will be used in the determination of baseline values, when applicable. This also applies to the primary efficacy variables derived from the VMS data collected in the subject diary, but on a weekly basis as described in the definition of the primary efficacy variables.

Primary Efficacy Variables:

The weekly frequency of moderate to severe VMS at baseline, week 4 and week 12, respectively, is defined as the total number (sum) of all recorded moderate to severe VMS experienced during the last 7 consecutive days during the Screening period (baseline), days 22 to 28 (week 4) and days 78 to 84 (week 12), respectively.

The mean severity score of VMS is defined as the arithmetic mean of the daily severity score values of VMS (moderate or severe) observed from days -7 to -1 at baseline and the arithmetic mean of the daily severity score values of VMS (mild, moderate or severe) observed during the days 22 to 28 and days 78 to 84 for week 4 and week 12 respectively.

At baseline, the daily severity score is computed as $[(2 \times \text{number of moderate VMS}) + (3 \times \text{number of severe VMS})] / (\text{total number of moderate + severe VMS})$ if at least one moderate to severe VMS was recorded during the day. In case of documented absence of moderate to severe VMS during the day, the daily severity will be set to zero.

Post-baseline (days 22 to 28 [Week 4] and days 78 to 84 [Week 12]), the daily severity score is computed as $[(1 \times \text{number of mild VMS}) + (2 \times \text{number of moderate VMS}) + (3 \times \text{number of severe VMS})] / (\text{total number of mild + moderate + severe VMS})$ if at least one mild to severe VMS was recorded during the day. In case of documented absence of VMS during the day, the daily severity will be set to zero.

The primary efficacy variables will be expressed as the changes from baseline computed as the differences between the estimated values at week 4 or 12 and the baseline values.

The daily severity score as defined above will also be recomputed for post baseline weeks as $[(2 \times \text{number of moderate VMS}) + (3 \times \text{number of severe VMS})] / (\text{Total number of moderate + severe VMS})$ if at least one moderate or severe VMS is recorded during the day.

The analysis including the mild VMS will be used for submission to the FDA, the analysis without the mild VMS will be used for submission to the EMA.

Analysis of Primary Efficacy Variables:

All statistical tests will be supported by presenting estimates and 95% CIs for the respective treatment effects (difference to placebo). These estimates and CIs will be based on the respective statistical models used for the analysis. Since all analyses of the efficacy variables are not exploratory in nature, adjustment for multiplicity will be performed (Dunnet adjustment for the comparison of each active dose versus placebo).

The primary efficacy comparison will test the following hypotheses for each treatment arm:

- H0: The average change from baseline in the primary efficacy endpoint in the treatment arm is greater (less pronounced) or equal to the average change from baseline in the placebo arm
- H1: The average change from baseline in the primary efficacy endpoint in the treatment arm is lower (more pronounced) to the average change from baseline in the placebo arm

The two dose groups of E4 will be compared to placebo regarding the four co-primary efficacy endpoints.

A comparison between treatment arms of the change from baseline at week 1 to week 12 in the weekly frequency of moderate to severe VMS and of the change from baseline in the weekly mean severity of moderate to severe VMS will be made by using Mixed-effect Models for Repeated Measures (MMRM). The MMRM models will include treatment, week, treatment by week interaction, and pooled trial centers as fixed effects and baseline as a covariate. If the pooled center effect included in the model is significant, a treatment by center interaction will be included in the model. Treatment effects will be assessed at Week 4 and 12 using two separate MMRM models (one on weekly frequency and another on weekly mean severity).

The primary analysis will use the data from the ITT population. Since an MMRM model is used, missing data imputation is not necessary. Additional sensitivity analyses will be implemented in order to assess the robustness of the results. These may include sensitivity with respect to:

- An imputation of missing data (last observation carried forward [LOCF] or other)
- The modeling strategy [analysis of covariance (ANCOVA) instead of MMRM]
- Confounders (for example ethnicity, hysterectomized status)
- Populations studied (mITT, PP)
- Any combination of the above

In addition, all primary efficacy variables will be tabulated at baseline and at each post-baseline time point.

Secondary Efficacy Variables:

In addition to all the secondary efficacy endpoints previously described, all the variables described above for the assessment of the primary objectives are also considered as secondary efficacy variables when evaluated at other time points than Week 4 and Week 12.

In addition, three VMS weekly weighted scores, taking into account both the frequency and the severity of VMS, will be computed based on the diary data as:

- $[(2 \times \text{number of moderate VMS}) + (3 \times \text{number of severe VMS})]$ for baseline and post baseline visits if at least one moderate to severe VMS was recorded and zero otherwise.
- $[(1 \times \text{number of mild VMS}) + (2 \times \text{number of moderate VMS}) + (3 \times \text{number of severe VMS})]$ for baseline and post baseline visits if at least one mild to severe VMS was recorded and zero otherwise.
- $[(2 \times \text{number of moderate VMS}) + (3 \times \text{number of severe VMS})]$ if at least one moderate to severe VMS was recorded for baseline visits and $[(1 \times \text{number of mild VMS}) + (2 \times \text{number of moderate VMS}) + (3 \times \text{number of severe VMS})]$ for post baseline visits if at least one mild to severe VMS was recorded and zero otherwise.

Furthermore, the severity score will also be recomputed as $[((1 \times \text{number of mild VMS}) + (2 \times \text{number of moderate VMS}) + (3 \times \text{number of severe VMS})) / (\text{total number of mild + moderate + severe VMS})]$ if at least one mild to severe VMS is recorded during the day for baseline and post baseline visits.

In case of documented absence of VMS during the day, the daily severity score will be set to zero. These additional efficacy variables will be derived for every week between baseline and week 12 based on the respective 7-day periods. All VMS related secondary efficacy variables will be expressed as changes from baseline computed as the differences of the estimated values at week 1 to 12 and the baseline values.

The percentage of subjects with a CID in the weekly frequency of moderate to severe VMS at weeks 4 and 12 will be assessed according to Gerlinger et. al. (Gerlinger C. et. al. Menopause. 2012 Jul; 19(7):799-803).

Analysis of Secondary Efficacy Variables:

All VMS related secondary efficacy variables will be analyzed using the same methodology as for the primary efficacy variables and will be based on the data from the ITT population.

All other secondary continuous efficacy variables will be analyzed using either an ANCOVA or a MMRM model depending on the type of endpoint considered. These models will be evaluated using data from the ITT, PP and mITT populations without imputation of data. Appropriate covariates may be included in the analyses.

The other categorical efficacy variables (scores, responder analysis) will be analyzed using appropriate statistical methods for the comparison of each treatment arm to the placebo arm.

In addition, all secondary efficacy variables will be tabulated by baseline and by each post-baseline time point.

Handling of Dropouts or Missing Data:

For days with missing VMS diary information, the number and intensity of VMS will be imputed with the mean values of the remaining days of the respective 7-day period, but only if at least 4 days with VMS data in this 7 day period are available. Otherwise, no calculation of the primary and related secondary efficacy variables will be done for this period.

No method of imputation is planned for the primary efficacy variable analysis since a MMRM model is used. As previously stated, sensitivity analyses of the primary efficacy variables may resort to imputation of missing data in order to assess the robustness of the MMRM results.

Safety parameters (safety set):

All safety parameters will be summarized using data from the Safety Analysis Set if not indicated otherwise. No formal statistical test will be performed to determine statistical significance between treatment groups. Continuous variables will be summarized using descriptive statistics (N, mean, standard deviation, median, minimum, maximum), categorical variables will be presented in frequency tables using counts and percentages. The frequency of endometrial events will be computed on the evaluable biopsies of the endometrium. The incidence of spotting/bleeding will be analyzed by a 28-day period. The incidence rate of endometrial events will be computed on the evaluable endometrium. The 95% two-sided CI will be computed on the observed frequency of hyperplasia/carcinoma of the endometrium.

Timing of analysis

The final analysis of the primary efficacy objective and the secondary efficacy objectives 1 and 2 of the Efficacy Study part will be triggered when all subjects in the Efficacy Study part have completed Visit 4. The analyses of all other efficacy and safety objectives from the Efficacy and Safety Study parts (including a final analysis of the safety objectives of the Efficacy Study part) will be triggered when the overall end of the trial is reached (i.e. when all subjects in the Efficacy Study part have completed Visit 8). The efficacy endpoints and the safety endpoints of the Safety Study will be analyzed separately from those of the Efficacy Study at the end of the Safety Study.

Synopsis Final Version 8.0, June 21, 2022

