Additional unscheduled visits may also be required during the treatment period for ad hoc safety assessments (e.g., TVUS for non-hysterectomized subjects).

Washout and Screening procedures for the Efficacy Study part and Safety Study part

At the Washout visit, after signing the informed consent, the inclusion and exclusion criteria will be checked as well as the prior medication list. If a subject uses prohibited co-medication, then this subject will be asked to stop this medication. After a variable washout period (depending on type of prior medication) the subject will return to start the screening procedures. For subjects who do not use medication that needs to be stopped and washed out, the Washout and Screening visit may occur at the same time. Screening includes a PAP test and mammography for all subjects, a TVUS for subjects with ovaries and/or uterus, and an endometrial biopsy for non-hysterectomized subjects. The length of the Screening period is generally up to 4 weeks, but can be extended (with prior Medical Monitor approval) without exceeding 8 weeks. During this period, and in addition to the screening procedures, the subject will record VMS in a paper diary. VMS data recorded during the last 7 consecutive days of the Screening period will be used to determine eligibility of subjects. If based on VMS symptoms of her current medical history a subject is only eligible for the Safety Study part, this subject may be enrolled directly into the Safety Study part without the VMS count in the Screening period, providing that all the screening assessments have been completed. Subjects who do not fulfill the VMS requirements for participation in the Efficacy Study

part, may participate in the Safety Study part, providing that they meet all other in- and exclusion criteria.

Treatment period Efficacy Study part

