5. For non-hysterectomized subjects: Endometrial biopsy taken during screening that reveals no abnormal results, i.e., presence of hyperplasia (simple or complex, with or without atypia), presence of carcinoma, and presence of disordered proliferative endometrium findings. The screening biopsy should have sufficient endometrial tissue for diagnosis. Biopsies without tissue or with insufficient tissue may be repeated once;
6. Seeking treatment for relief of VMS associated with menopause;
 - a. For the Efficacy Study part: at least 7 moderate to severe bothersome VMS per day or at least 50 moderate to severe bothersome VMS per week in the last 7 consecutive days during the Screening period¹;
 - b. For the Safety Study part: at least 1 moderate to severe VMS per week;
7. Body mass index $\geq 18.0 \text{ kg/m}^2$ up to $\leq 38.0 \text{ kg/m}^2$;
8. A mammogram that shows no sign of significant disease performed during screening or within 9 months prior to the start of screening²;
9. Postmenopausal status defined as any of the following:
 - a) For non-hysterectomized subjects:
 - at least 12 months of spontaneous amenorrhea with serum follicle stimulating hormone (FSH) $>40 \text{ mIU/ml}$ (value obtained after washout of estrogen/progestin containing drugs, see exclusion criteria 18 and 20);
 - or at least 6 months of spontaneous amenorrhea with serum FSH $>40 \text{ mIU /mL}$ and E2 $<20 \text{ pg/mL}$ (value obtained after washout of estrogen/progestin containing drugs, see exclusion criteria 18 and 20);
 - or at least 6 weeks postsurgical bilateral oophorectomy³;
 - b) For hysterectomized subjects:
 - serum FSH $>40 \text{ mIU/mL}$ and E2 $<20 \text{ pg/mL}$ (values obtained after washout of estrogen/progestin containing drug see exclusion criteria 18 and 20);
 - or at least 6 weeks postsurgical bilateral oophorectomy³;
10. Good physical and mental health, in the judgement of the Investigator as based on medical history, physical and gynecological examination, and clinical assessments performed prior to Visit 1;
11. Able to understand and comply with the protocol requirements, instructions, and protocol-stated restrictions;
12. Able and willing to complete trial daily diaries (if applicable, see Section 10.1.7) and questionnaires.

Exclusion Criteria:

Subjects will not be allocated to treatment if they meet one of the following exclusion criteria:

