- g) To be performed in subjects with uterus and/or cervix, unless a written normal result is available within 18 months before screening start. The PAP test may be repeated once in case of inadequate or insufficient sample.
- h) Non-hysterectomized subjects only.
- i) If the subject was treated for at least 12 weeks
- j) TVUS at screening and EoT will be taken for all subjects who still have a uterus and/or ovaries. At all other time points a TVUS will be performed to monitor the endometrium thickness only for subjects who still have a uterus.
- k) Unless a written normal result is available within 9 months before screening start.
- l) Mammography at EoT visit may only be performed if the subject was treated for at least 12 weeks and the last mammography was taken at least 9 months earlier
- m) If the subject is not fasting, a new appointment needs to be made as soon as possible. Laboratory tests may be repeated once during the screening period, at the discretion of the investigator.
- n) Additional blood samples including one DNA sample at Visit 1 only, will be collected for optional additional analysis of in the context of this program or any further research on E4.
- o) A pregnancy test may be performed at the discretion of the Investigator.
- p) VMS will be recorded daily in the paper diary during the Screening period and during the treatment period up to Visit 4.
- q) During VMS recording subjects will be reminded weekly (phone, e-mail, SMS etc.) to complete the diary. The first reminder will be sent 5 ± 2 days after start of VMS recording.
- r) Subjects are instructed during screening on how to fill in the diary and if needed can be re instructed.
- s) At each visit the diary will be checked. Completed pages will be collected and will remain at the study site.
- t) Progestin treatment for non-hysterectomized subjects only.
- u) If lipid and/or glucose parameters could be a reason of concern in the judgement of the Investigator, fasted blood sampling for lipid and glucose parameters assessment may be done during the Washout Visit. Otherwise, this assessment will be done during the screening period.
- v) Laboratory tests may be repeated once during the screening period, at the discretion of the investigator. FSH measurement is not required for subjects with bilateral oophorectomy.

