10.1.3. Screening Visit (Within 4 weeks before Randomization/Treatment allocation)

After the washout period (if applicable) the participant will come to the Screening visit marking the beginning of the Screening period. The Screening period will last up to 4 weeks and the visit needs to occur within 4 weeks prior to Visit 1). The following procedures will be performed as screening procedures:

- Review of already available inclusion and exclusion criteria
- Physical examination
- Gynecological examination
- Breast examination
- Vital signs
- 12-lead ECG
- PAP test (unless a written normal result is available within 18 months before the start of screening)
- TVUS (for women who still have uterus and/or ovaries)
- Endometrial biopsy (for non-hysterectomized women only)
- Digitalized mammography (unless a written normal result is available within 9 months before the start of screening)
- Modified MENQOL questionnaire
- Fasted blood sampling for:
 - Routine hematology and chemistry
 - Lipid and glucose parameters for inclusion (if not done as Washout visit)
 - FSH, E2 and TSH for inclusion (fasting not required)
- Urinary pregnancy test (at the discretion of the Investigator)
- Dispense and explain paper diary
- Record prior medication and start recording concomitant medication.
- Start recording AEs.

The screening period may require additional visits for some assessments (i.e., mammography, biopsy, TVUS, ECG, PAP test) in case these assessments cannot be done during the Screening visit.

During screening the subjects will receive a paper diary and are instructed to record the severity and frequency of VMS until return for Visit 1. The study personnel will remind the subjects weekly (by phone, SMS, e-mail etc.) to complete the diary. The first reminder will be sent 5 ± 2 days after start of VMS recording (i.e. screening visit).

In case it is clear during screening that a subject will participate in the Safety Study part, either because she does not present a score of 4 to 6 on question 1 of the modified MENQOL questionnaire at screening, or based on current medical history, she will not reach the VMS requirements to participate in the Efficacy Study part or because the enrollment in the Efficacy Study part has been completed, the recording of VMS symptoms in the paper diaries may be skipped. The subject will return for Visit 1 after all screening results are available.

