12.5. Analysis of Primary Efficacy Variables

All statistical tests will be supported by presenting estimates and 95% CIs for the respective treatment effects (difference to placebo). These estimates and CIs will be based on the respective statistical models used for the analysis. Since all analyses of the efficacy variables are not exploratory in nature, adjustment for multiplicity will be performed (Dunnet adjustment for the comparison of each active dose versus placebo).

The primary efficacy comparison will test the following hypotheses for each treatment arm:

- H0: The average change from baseline in the primary efficacy endpoint in the treatment arm is greater (less pronounced) or equal to the average change from baseline in the placebo arm
- H1: The average change from baseline in the primary efficacy endpoint in the treatment arm is lower (more pronounced) to the average change from baseline in the placebo arm

The two dose groups of E4 will be compared to placebo regarding the four co-primary endpoints.

A comparison between treatment arms of the change from baseline at week 1 to week 12 in the weekly frequency of moderate to severe VMS and of the change from baseline in the weekly mean severity of moderate to severe VMS will be made by using Mixed-effect Models for Repeated Measures (MMRM). The MMRM models will include treatment, week, treatment by week interaction and pooled trial centers as fixed effects and baseline as a covariate. If the pooled center effect included in the model is significant, a treatment by center interaction will be included in the model. Treatment effects will be assessed at week 4 and 12 using two separate MMRM models (one on weekly frequency and another on weekly mean severity).

The primary analysis will use the data from the ITT population. Since an MMRM model is used, missing data imputation is not necessary. Additional sensitivity analyses will be implemented in order to assess the robustness of the results. These may include sensitivity with respect to:

- An imputation of missing data (last observation carried forward [LOCF] or other)
- The modelling strategy [analysis of covariance (ANCOVA) instead of MMRM]
- Confounders (for example ethnicity, hysterectomized status)
- Populations studied (mITT, PP)
- Any combination of the above

In addition, all primary efficacy variables will be tabulated at baseline and at each post-baseline time point.

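### The primary VMS models adjust only for the last 7 screening days and leave the earlier screening diary unused, a modest loss of precision and not a bias

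*Protocol*

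**What the plan says.** The schedule for the Efficacy Study part (protocol 2.1, footnote p) states that "VMS will be recorded daily in the paper diary during the Screening period and during the treatment period up to Visit 4". Section 10.1.3 has women "instructed to record the severity and frequency of VMS until return for Visit 1". On duration, the Synopsis says "The length of the Screening period is generally up to 4 weeks", extendable to 8 weeks with approval; no minimum is given. Section 10.1.7 sends the diary data to the eCRF, and 9.6.1 requires washout to be complete before screening starts.

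Only the final week is then used. For eligibility, "VMS data recorded during the last 7 consecutive days of the Screening period will be used to determine eligibility of subjects"; criterion 6a asks for at least 7 events per day or "at least 50 moderate to severe bothersome VMS per week in the last 7 consecutive days during the Screening period". The frequency variable is the count over the same days at baseline, being the moderate to severe VMS "experienced during the last 7 consecutive days during the Screening period (baseline), days 22 to 28 (week 4"), and the severity baseline is the mean daily score "observed from days -7 to -1 at baseline" (Synopsis; 12.4).

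Section 12.5 fits one MMRM for frequency and one for severity, each with treatment, week, their interaction and "pooled trial centers as fixed effects and baseline as a covariate". Its possible sensitivity analyses name ethnicity and hysterectomy status as extra covariates, but not the earlier diary.

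**The concern.** A single week's count is a noisy reading of a woman's usual VMS level. Where counts vary from week to week around that level, earlier screening days say something about her Week 4 and Week 12 counts that the last week does not. Leaving them out makes residual variance larger than it need be.

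Precision matters here. The plan claims at least 80% power to win on four co-primary endpoints together (8.1.1). It expects 35% and 20% dropout by Week 12 in non-hysterectomized and hysterectomized women. Section 7.1.3.3 also reports that the Phase 2 frequency reduction at 15 mg missed statistical significance. The data that could help cost nothing further to collect.

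**Working it through.** **The plan's own figures.** Completers at Week 12: 300 × 0.65 + 300 × 0.80 = 195 + 240 = 435, which matches 8.1. That is 145 per arm, or 290 per dose-placebo contrast. The power of at least 80% cannot be reproduced, because no effect size, SD or endpoint correlation is stated.

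**General form.** Let ρ be the correlation of the last-week count with the outcome, and r the correlation between screening weeks, all weeks being exchangeable. Neither is in the documents. Adjusting for one week leaves residual variance proportional to 1 − ρ². With k screening weeks in total, ρₖ² = ρ²k / (1 + (k − 1)r), and the variance ratio is (1 − ρₖ²)/(1 − ρ²).

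| k | r | ρ | ρₖ² | Variance ratio |
|---|---|---|---|---|
| 4 | 0.9 | 0.3 | 0.09 × 4/3.7 = 0.097 | 0.903/0.91 = 0.992 |
| 4 | 0.8 | 0.4 | 0.16 × 4/3.4 = 0.188 | 0.812/0.84 = 0.966 |
| 4 | 0.7 | 0.4 | 0.16 × 4/3.1 = 0.206 | 0.794/0.84 = 0.945 |
| 2 | 0.7 | 0.4 | 0.16 × 2/1.7 = 0.188 | 0.812/0.84 = 0.966 |

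Two weeks in total therefore give about 60% of the four-week gain (0.034 against 0.055).

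Simulation added two facts:

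- Selecting women on the last week moves these ratios by only about 0.002.
- If weeks follow a first-order autoregression and the outcome depends only on the last week, adding the earlier mean gives a ratio of 1.000. Replacing the last week by a 4-week mean gives 1.03 to 1.17, a loss.

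**Anchored to the protocol.** Section 7.1.3.3 reports Phase 2 VMS reductions of 65% (placebo) and 84% (E4 15 mg), so remaining fractions are 1 − 0.65 = 0.35 and 1 − 0.84 = 0.16.

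Assumptions:

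- the 20 mg fraction equals that of 15 mg;
- between-woman CV 45% and week-to-week CV 15-35%;
- SD of the remaining fraction 0.15-0.30;
- entry at 50 or more in the last week.

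Change at Week 12 was regressed on the last-week count with and without the earlier-week mean.

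| Earlier diary | Fall in Week 12 frequency residual variance |
|---|---|
| Three earlier weeks | about 1-6% |
| One earlier week, or strongly autocorrelated weeks | about 0.7-3% |

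**Power for one contrast set at 80%.** Power = Φ(2.80/√ratio − 1.96), where 2.80 = 1.96 + 0.84.

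- Ratio 0.99: Φ(2.814 − 1.96) = Φ(0.854) ≈ 0.80.
- Ratio 0.94: Φ(2.888 − 1.96) = Φ(0.928) ≈ 0.82.

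In completers on that contrast: 290 × (1/0.99 − 1) ≈ 3 to 290 × (1/0.94 − 1) ≈ 19.

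**The case against.** The strongest reply is that this is an optional refinement. The last-7-day baseline is valid, matches the eligibility window, and defines the change score. Four weeks is a ceiling with no stated minimum, so some women may have few earlier days. The addition also brings a correlated covariate, a fill-in value and an indicator into each model. All of this stands and keeps the point small, but it does not remove it: the gain shrinks with shorter diaries and reaches zero only in the limiting case above.

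A reader might infer more in four places.

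- **Selection.** Because the baseline week also decides entry, it is tempting to call it inflated, the noisiest week, or a source of bias. Regression to the mean after selection is shared by the randomized arms, selection barely changes the variance ratios, and nothing shows that week to be noisier than the others.
- **Size.** Remaining fractions of 0.35-0.60 give a 3-11% variance reduction and up to about 84% power. Section 7.1.3.3 puts placebo at the bottom of that range and E4 15 mg well outside it.
- **All co-primaries.** Only Week 12 frequency was simulated. Eligibility is a count. Baseline severity lies between 2 and 3 on any day with a moderate or severe event, while the post-baseline score can fall to 0. A frequency result cannot be carried over to severity.
- **Omission from the final plan.** The supplied SAP covers the Safety Study part only. It cites an Efficacy Study Part SAP, version 3.0, whose covariates cannot be seen here.

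**Conclusion.** The point holds as a modest efficiency improvement. The protocol collects daily pre-randomization VMS data beyond the last week and uses none of it in the primary models.

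The expected gain in Week 12 frequency residual variance is a few percent at most under the Phase 2 response figures. It is larger if more VMS remain on treatment, and near zero if the last week carries all the prognostic information. These figures depend on assumed CVs and on an assumed response at 20 mg, none of which the documents give.

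The 80-82% figure is for a single contrast. It is not the power for four endpoints together, which cannot be recomputed.

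**What to change.** Keep the endpoint as change from the last 7 screening days, and keep that week as a covariate. In 12.5, the Synopsis and the Efficacy SAP (if not already there), add a second covariate:

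- **Frequency MMRM:** the mean daily count of moderate to severe VMS over screening-diary days before the last 7.
- **Severity MMRM:** the mean daily severity score over the same days, computed as at baseline.
- **Fewer than 4 such days:** set the covariate to the last-7-day mean and include an indicator. Four days is also the minimum that 12.3 sets for a 7-day period.

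Do not replace the last-7-day baseline with a longer mean, which can lose precision.

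Fix this before the unblinded analysis triggered when all Efficacy subjects complete Visit 4 (12.9). After that, report it only as a labelled sensitivity analysis. The cost is one derived variable per model from data already collected, plus the fill-in rule, the indicator and a line of model wording.
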